10.2 Outcome analysis

Cumulative survival is calculated according to the Kaplan-Meier method [21], indicating the 95% confidence interval. Descriptive analysis to summarize the data and study results will be carried out by calculating mean, standard deviation and range of minimum and maximum values for continuous variables and by number and percentage for dichotomous variables. Data distribution was tested for normality with Shapiro-Wilk and D'Agostino Pearson tests.

The analysis of survival rates with 95% confidence intervals of study group versus control group will be performed with logarithmic rank test placing statistical significance at a p-value < 0.05.

The analysis of the differences between the 2 groups regarding the continuous variables will be carried out with Student's t test, while Mann-Whitney U test was used when distribution resulted not normal. The analysis of differences in dichotomous variables will be carried out with Chi-Square or Fisher's Exact tests if at least one of the variables has a value ≤ 5 .

The analysis will be carried out with one of the most used statistical software for this type of analysis (GraphPad Prism 10.1.0 Software, Boston, MA, USA).

11. Ethical and regulatory considerations

This clinical investigation is conducted in compliance with the ethical principles set out in the Declaration of Helsinki [22].

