4.1 Primary endpoint

The primary objective of the study is to verify that the survival of the prosthetic implant with vitamin E polyethylene is not inferior to the survival of the prosthetic implant with conventional polyethylene. The primary endpoint is therefore the cumulative implant survival, defining revision for aseptic loosening as the endpoint (or failure).

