10.1 Sample size

In order to calculate the sample size of the study group and the control group, a non-inferiority study is chosen as the most suitable type. Since in the medium term (5-7 years of follow-up), there is reasonably no expectation of significantly better survival results when using a vitamin E polyethylene articular insert compared to a standard polyethylene insert, but rather comparable results. Therefore, we choose to calculate the sample size of the groups using a statistical test of non-inferiority for binary variables (failed implant vs survived implant) of 2 paired groups.

From the prosthetic joint replacement registries of Australia and UK, reports of 2019 and 2018 respectively, the cumulative percentage of revision in total knee arthroplasty with mobile insert is reported as 2.77% at 5 years of follow-up [NJR Report 2018] and 2.8% for HXPE polyethylene inserts at 5 years of follow-up [AUS Report 2019]. The Australian registry also reports 2.3% as the cumulative revision rate for total knee arthroplasty with an insert supplemented with vitamin E at 5 years of follow-up. A difference of at least 4% is considered clinically relevant between survival rates of different knee implants.

Using these failure/survival rates for the control group and the treatment (vitamin E) group, choosing a significance level (alpha) of 5%, a power of 80%, a survival rate of 97.2% for the control and 97.7% for the vitamin E group and with 4% as margin of non-inferiority between both groups, the calculation provides 152 implants per group.

<https://www.sealedenvelope.com/power/binary-noninferior/>

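### The primary question is non-inferiority with a 4-point margin, but the only planned comparison of survival is a log-rank test of equality, which cannot answer it

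*Combined protocol and SAP*

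**What the plan says.** Section 4.1 states that the primary objective is to "verify that the survival of the prosthetic implant with vitamin E polyethylene is not inferior" to that of the conventional insert. The endpoint is cumulative implant survival, with revision for aseptic loosening as failure. No analysis time is given.

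Section 10.1 explains the design choice: in the medium term "there is reasonably no expectation of significantly better survival results" with the vitamin E insert. The sample size therefore uses a "statistical test of non-inferiority for binary variables (failed implant vs survived implant) of 2 paired groups", with alpha 5%, power 80%, survival of 97.2% (control) and 97.7% (vitamin E), and "with 4% as margin of non-inferiority between both groups". The result is 152 implants per group.

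Section 10.2 gives the analysis: "Cumulative survival is calculated according to the Kaplan-Meier method [21], indicating the 95% confidence interval", and then "The analysis of survival rates with 95% confidence intervals of study group versus control group will be performed with logarithmic rank test", with significance at p < 0.05. Its other tests (t, Mann-Whitney, chi-square, Fisher) are also tests of difference.

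**The concern.** The objective and the sample size belong to one hypothesis, the analysis to another. Non-inferiority requires rejecting the hypothesis that the vitamin E insert is worse by 4 points or more. The log-rank test can only reject the hypothesis that the two survival curves are equal. The margin appears in 10.1 as a sample-size input and is not used again.

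The confidence intervals in 10.2 do not close the gap. They attach to the survival estimates, and no interval for the difference between groups is named. Nor is there a time at which to read the difference: the registry rates are at 5 years, 10.1 calls the medium term 5 to 7 years, and 6.3 requires at least 7 years of follow-up.

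The data could answer the question, but the rule would have to be chosen after they are seen, by the sponsor, which section 8.3 makes responsible for the analysis. Because 10.1 expects the two inserts to perform alike, treating a non-significant log-rank as confirmation is a foreseeable reading.

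**Working it through.** **Inputs.** From 10.1: control failure 2.8% (survival 97.2%), vitamin E failure 2.3% (97.7%), margin 4 points, alpha 5%, power 80%, 152 per group. From 10.2: log-rank at p < 0.05, taken as two-sided. Assumptions: every knee followed in full, independent groups, exponential failure times in the log-rank simulations.

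**1. The plan's own figure.** n per group = (z_alpha + z_beta)² × (0.023 × 0.977 + 0.028 × 0.972) / (0.005 + 0.04)².

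- One-sided 5%: 6.183 × 0.049687 / 0.002025 = 151.7, so 152. This reproduces the plan.
- One-sided 2.5%: 7.849 × 0.049687 / 0.002025 = 192.6, so 193.

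So 152 corresponds to a one-sided 5% test, equivalent to a two-sided 90% interval. The formula is for independent groups, although 10.1 calls them paired.

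**2. Information available.** Expected failures are 152 × (0.028 + 0.023) = 7.8 at the planned rates, and 152 × (0.028 + 0.068) = 14.6 if vitamin E is exactly 4 points worse.

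**3. What the equality test does.** Log-rank: 20,000 simulated trials per row. Check: exact enumeration of the two-proportion z test.

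| True failure, control vs vitamin E | Log-rank p < 0.05 | z test, exact | Non-significant |
|---|---|---|---|
| 2.8% vs 2.3% (planned) | 0.055 | 0.052 | about 95% |
| 2.8% vs 6.8% (at margin) | 0.375 | 0.371 | about 63% |
| 1% vs 5% (at margin) | 0.538 | 0.542 | about 46% |
| 5% vs 9% (at margin) | 0.270 | 0.268 | about 73% |

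The 1% and 5% control rates are assumptions that show a range. The documents give no rate for aseptic loosening, and 2.8% is a 5-year registry revision rate.

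**4. What a margin rule does.** Exact probability that the upper bound of the difference (vitamin E minus control failure) is below 4 points, 152 per group:

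| True failure, vitamin E vs control | Wald 90% | Wald 95% | Newcombe 90% | Newcombe 95% |
|---|---|---|---|---|
| 2.3% vs 2.8% (power) | 0.821 | 0.697 | 0.752 | 0.584 |
| 6.8% vs 2.8% (false pass) | 0.066 | 0.033 | 0.052 | 0.020 |
| 5% vs 1% (false pass) | 0.089 | 0.049 | 0.048 | 0.018 |

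**5. Single results.**

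- 11 failures with vitamin E against 4 with control: difference 7/152 = 4.6 points, past the margin. The log-rank p is 0.059 to 0.070 depending on event times. The 90% upper bound is 8.7 (Wald) or 9.1 (Newcombe) points.
- 10 against 4: difference 6/152 = 3.9 points, equality p about 0.10, 95% Wald upper bound 8.6 points. Non-inferiority is not shown, yet nothing is significant.
- 5 against 4: the 90% upper bound is 3.9 (Wald, passes) or 4.3 (Newcombe, fails). The interval method can decide the result.
- 0 against 0: the Wald interval has zero width, while the Newcombe upper bound is about 1.7 points.

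**The case against.** Section 10.1 does fix in advance the type of hypothesis, a binary non-inferiority test, alpha and the margin, so the plan is not blank. That is true, but those choices are never carried into 10.2, which names a different test, and they leave the time point and the interval open.

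The 63%, 46% and 73% depend on reading p ≥ 0.05 as non-inferior, which the protocol nowhere says. That is also true. They show the consequence of one foreseeable reading. The mismatch itself does not depend on it.

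The figures hold the sample at 152, which the protocol calls a minimum. With 300 per group, the 63% falls to about 36%, which is smaller but still far above 5%.

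The 11-against-4 result is an extreme case. A non-significant test with an observed deficit of 4 points or more occurs in about 8% of trials at 6.8% against 2.8%. More often the observed deficit is below 4 points and the interval crosses the margin, as with 10 against 4. The log-rank test is silent about that too.

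Finally, the power figures treat survival as a simple proportion with complete follow-up. Deaths and losses would change them for a Kaplan-Meier difference, so they are approximations.

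**Conclusion.** The concern holds, and the plan should be corrected before the analysis. This is not missing detail: the test named in 10.2 addresses a different hypothesis from the one in 4.1 and 10.1, and neither of its outcomes supports or refutes non-inferiority at 4 points. The 152 per group is correct for a one-sided 5% test.

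At 152 per group with full follow-up, reading a non-significant log-rank as success would pass an insert that is exactly at the margin in about 63% of trials at the protocol's control rate (46% to 73% for assumed control rates of 1% to 5%). At the planned rates the log-rank is non-significant in about 95% of trials, whereas a 90% interval would clear the margin in about 82% (Wald) or 75% (Newcombe). The two rules are not interchangeable even when the planning assumptions are right.

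**What to change.** Replace the comparison in 10.2 with a primary analysis that states:

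- the estimate: the difference in Kaplan-Meier failure probability, vitamin E minus control, for revision due to aseptic loosening;
- the time at which it is read, for example 7 years, the minimum follow-up in 6.3;
- the interval method, suited to few events, and its level: a two-sided 90% interval matches 152 per group, while a two-sided 95% interval corresponds to 193;
- the rule: non-inferiority is concluded only if the upper bound is below 4 points;
- the log-rank test as descriptive only.

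The choice of interval is the sponsor's, provided it is fixed in advance. The power of that choice at 152 per group should be stated beside it. As complete-follow-up approximations at the planned rates, it is about 82% (90% interval) or 70% (95%) with Wald limits, and about 75% or 58% with Newcombe-type limits.

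The cost is one paragraph, with no new patients or data needed to specify the rule. The drawback is that the 80% power claim may not survive. With Newcombe-type limits, 80% is first reached at about 174 per group (90% interval) or 232 (95%). Both are approximate, since power does not rise smoothly with so few events. Because 152 is a minimum, any further eligible knees would recover part of the loss.

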Exclusion criteria	
 Patient who received knee prosthesis different from Permedica's GKS Prime Flex Mobile Bioloy. Patients already included in other clinical investigations. Patients who do not sign the informed consent.
Telephone contact	Telephone contact of all eligible patients for recording FJS-12, any adverse events, if lost to follow-up or deceased and for scheduling the follow-up visit.
Follow-up visit	Physical examination, AKSS compilation, FJS-12, recording of complications, adverse events, radiographic assessment for periprosthetic radiolucent lines and osteolysis.

2. Introduction and state of the art

One of the most limiting factors for the longevity of a prosthetic implant in hip and knee arthroplasty is the resistance to wear and degradation of the polyethylene acetabular inserts.

The degradation of ultra-high molecular weight polyethylene (UHMWPE) is that process whereby there is an alteration of the chemical structure of the material with a decrease in the molecular weight. Degradation decreases the mechanical characteristics of the polyethylene and, therefore, potentially reduces the longevity of the polyethylene joint insert. Degradation occurs when the polymeric material is exposed to a quantity of energy greater than that of the chemical bonds of which the polymer chains are made up, so that some chemical bonds are broken. and new free radicals are created. This process in the presence of oxygen is called oxidative degradation or more simply oxidation. Once triggered, the oxidative process is irreversible and self-sustaining with the formation of new radicals that react with oxygen, thus creating a chain reaction.

In orthopaedics, polyethylene acetabular inserts are typically subjected to high doses of energy in the form of irradiation with the aim of increasing the degree of cross-linking or sterilizing the device. This radiation, through the splitting of bonds within the polymer chains, produces the formation of active free radicals within the material. Most free radicals recombine, forming new bonds in the amorphous phase of polyethylene, i.e. cross-linking. The free radicals formed inside the crystalline phase remain trapped for a long time and are responsible for oxidation [1-3].

Stabilization with vitamin E

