Furthermore, nothing has yet been published in the literature on mid-term results in primary total knee arthroplasty with polyethylene insert added with vitamin E. The maximum follow-up reported from clinical studies in total knee arthroplasty is in fact 3 years.

A study that reports the medium-term results of a series of total knee arthroplasties using polyethylene with vitamin E and comparing them with those of an identical insert but made of conventional polyethylene is therefore considered scientifically valid and well-founded.

The present study therefore aims to verify the survival, clinical and radiographic results of a consecutive series of patients undergoing first-time total knee arthroplasty with a polyethylene insert added with vitamin E, comparing them with an identical insert but made of polyethylene standard, at a minimum follow-up of 7 years.

3. Study design

Observational, cross-sectional, comparative, monocentric clinical study with a retrospective cohort. The study is promoted and sponsored by Permedica S.p.A., [name], Italy <https://www.permedica.it/>. The study centre is the Quadrante Orthopaedics Center (C.O.Q.) Hospital, placed in [name] - Italy. Study principal investigator (PI) will be [name]. The study will be conducted by PI and other co-investigators, PI's collaborators of the Orthopaedics Unit at C.O.Q. Hospital in Omegna and external collaborators of the CTO Hospital of Turin, coordinated by [name], Director of the Orthopaedics Unit and Traumatology 1, CTO Hospital of Turin. The study, being observational, will only concern

the collection of data about the patient, his medical history and pathology, his surgery and prosthetic implant and the clinical and radiographic results. The patient will be contacted by telephone and invited to a follow-up visit. Clinical scores will be recorded by the patient and the investigators, radiographic signs will be recorded from preoperative and postoperative radiographs performed at the last follow-up. The study will therefore not require any additional diagnostic or therapeutic services compared to the standard clinical practice. The study will only take into consideration patients who have already undergone total knee arthroplasty at the C.O.Q. Orthopaedics Unit.

4. Study objective

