7.3 Follow-up visit

At the follow-up visit, an objective evaluation of the operated knee will be carried out, questions will be asked about the patient's current state of health, as well as a radiographic follow-up evaluation will be carried out assessing the last anterior-posterior and lateral knee radiographs compared with the first postoperative radiograph.

If the patient has signed the Informed Consent and the Consent to the Processing of Personal Data, the information requested in the case report forms described below will be recorded.

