8.1 Case Report Forms (CRF)

For data recording according to this protocol, specific data collection forms, or case report forms (CRF), are prepared. The information reported in anonymous fashion on the CRFs must be recorded for each patient included in the study. Patients will be identified through their name/surname initials following a progressive number. Only the principal investigator will know the 1:1 association between patient and his ID. The CRFs, annexed to this protocol, are the following:

1. Medical history. General data of the patient, age, weight, height, diagnosis, medical history, previous medical history, known allergies, osteoporosis.
2. Intervention. Prosthetic implant information, the operation date, tibial insert material, whether conventional polyethylene without vitamin E or vitamin E polyethylene (respectively, control group or treatment group), are recorded.
3. AKSS. Knee-specific clinical evaluation score that the investigator completes at the last follow-up during the patient's follow-up visit [19].
4. FJS-12. Clinical evaluation score on the patient's awareness on his prosthesis, to be filled by the patient himself at the last follow-up [20].
5. Radiographic evaluation. Form that the investigators complete by evaluating and comparing the first postoperative radiograph taken after surgery and the anterior-posterior and lateral knee radiographs taken at the last follow-up. The radiographic signs showing the presence of any periprosthetic radiolucency lines or areas of periprosthetic osteolysis, signs of prosthetic loosening and component position will be recorded for each periprosthetic zone according to the "Modern Knee Society Radiographic Evaluation System and Methodology for Total Knee Arthroplasty".

6. Complications. Form to be completed in case of presence of one or more intraoperative or postoperative complications recorded through assessment of the patient's medical records, or at the first telephone contact or during the follow-up visit.

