11.2 Ethical considerations on the patient

The study aims to verify the survival, results, safety and reliability of a particular prosthetic device used in total knee arthroplasty. This is a cross-sectional study with a retrospective cohort and it will not involve any additional treatment for the patient. The patient has already undergone primary total knee arthroplasty with the investigational device according to the standard procedures provided by the C.O.Q. Orthopaedics Unit. The patient will only be contacted in order to receive his consent to participate in the study, for the compilation of a subjective evaluation form and for the collection of his clinical and radiographic data from visits and radiographic follow-ups normally carried out during normal clinical practice.

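### Section 10.2 compares non-randomised insert groups only with unadjusted tests that treat knees as independent, and gives no rule for bilateral patients

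*Combined protocol and SAP*

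**What the plan says.** Section 3 describes the design as "Observational, cross-sectional, comparative, monocentric clinical study with a retrospective cohort". The groups are defined by the insert received at surgery.

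Section 10.2 is the whole analysis plan. Survival is estimated by Kaplan-Meier and compared by log-rank at p < 0.05. For scores, "The analysis of the differences between the 2 groups regarding the continuous variables will be carried out with Student's t test", or Mann-Whitney if the distribution is not normal. Dichotomous outcomes get chi-square or Fisher tests. No regression, stratification, weighting, matching or clustered variance is mentioned.

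Section 8.1 lists what is collected. Form 1 holds "General data of the patient, age, weight, height, diagnosis, medical history, previous medical history, known allergies, osteoporosis"; form 2 holds "Prosthetic implant information, the operation date, tibial insert material".

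On timing, section 6 sets surgery between January 2011 and December 2015, and section 6.3 requires at least 7 years of follow-up with no upper limit. AKSS is completed at the follow-up visit. Section 8.1 says the FJS-12 is "to be filled by the patient himself at the last follow-up", while the synopsis lists it under both the visit and the telephone call: "Telephone contact of all eligible patients for recording FJS-12, any adverse events".

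Sections 6.1 and 6.2 count each group in knees (at least 152). Neither section 6.3 nor section 10.2 says what happens when a patient has both knees replaced. Section 10.1 calls the two groups paired.

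**The concern.** Without randomisation, the groups can differ in age, body mass, diagnosis, bone quality and period of surgery. An unadjusted test attributes any resulting difference in AKSS, FJS-12, radiolucency or complications to the insert. A baseline table would reveal an imbalance but would not correct it.

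Implant age is a specific case. Scores and films are read once, at last follow-up, on implants placed over a 5-year window. If one insert was used earlier on average, its knees are assessed later after surgery and usually in older patients. Kaplan-Meier and log-rank work on time since surgery, so they deal with unequal follow-up length for survival. The tests for scores and radiographs do not.

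The tests also assume independent knees. Two knees of one patient in the same group make p-values too small; two knees in opposite groups make the unpaired tests conservative.

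**Working it through.** **1. The plan's own figure.** Section 10.1 gives survival of 97.2% (control) and 97.7% (vitamin E), a 4-point margin, alpha 5%, power 80%, and 152 per group. The formula for two independent groups with one-sided alpha 5% is

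n = (1.6449 + 0.8416)² × (0.972 × 0.028 + 0.977 × 0.023) / (0.04 + 0.005)² = 6.1827 × 0.049687 / 0.002025 = 151.7, rounded up to 152.

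The figure therefore reproduces for independent groups. Section 10.1 describes the groups as paired, but no matching procedure is given and every test in 10.2 is unpaired.

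**2. Bias in a score comparison.** With 152 knees per group, SE = √(2/152) = 0.1147 SD. For a bias of d SD, the two-sided error is P(|Z + d/SE| > 1.96).

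- d = 0.1: shift 0.87, error 0.141.
- d = 0.2: shift 1.74, error 0.414.

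The range is assumed. One way to reach it is a 0.3 SD imbalance in a covariate worth 0.3 SD per SD (0.09 SD), plus a 0.75-year gap in implant age at 0.05 to 0.10 SD per year (0.0375 to 0.075 SD). Together these give about 0.13 to 0.17 SD.

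**3. Bilateral knees.** If a share b of patients is bilateral, the share of knees in pairs is f = 2b/(1 + b): 0.182 at b = 10% and 0.462 at b = 30%. Assume a within-patient correlation (ICC) of 0.3 to 0.7.

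| Pairs | Variance factor | Range | Error, 2P(Z > 1.96/√factor) |
|---|---|---|---|
| Same group | 1 + f × ICC | 1.055 to 1.323 | 5.6% to 8.8% |
| Opposite groups | 1 − f × ICC | 0.945 to 0.677 | 4.4% to 1.7% |

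**4. Cost of adjusting for time since surgery.** Assume surgery dates uniform over 60 months and visits uniform over 12 months. The variance of time since surgery is 60²/12 + 12²/12 = 312 months². If a share p of one insert falls in the first half of the window and a share p of the other in the second half, the mean gap is (2p − 1) × 30 months. Then R² = [(2p − 1) × 15]²/312, and the SE of the group effect grows by 1/√(1 − R²).

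- 65/35 split: R² = 0.065, factor 1.03.
- 80/20 split: R² = 0.26, factor 1.16.
- Fully sequential use: R² = 0.72, factor 1.89.

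**5. Room to adjust survival.** At the 5-year revision rates in section 10.1, 152 × (0.028 + 0.023) = 7.8 events are expected. The number at 7 years or more, and the number due to aseptic loosening, are not given.

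**The case against.** The strongest reply is that no bias has been demonstrated and that the design already restricts confounding: one centre, a consecutive series, the same cemented prosthesis, and the same insert geometry. This stands in part. Restriction removes hospital and implant differences, but not case mix or era of surgery. The sizes above are consequences of assumed inputs, and section 10.2 states a 0.05 threshold only for the log-rank test; applying 5% to the scores is an assumption here.

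A second reply is that so few revisions cannot support covariate adjustment. For survival this is right, and the fix does not ask for it.

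Stronger readings are tempting, and the documents do not support them:

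- *A computable inflation of false non-inferiority for the primary endpoint.* Such a figure would evaluate the margin formula of section 10.1. Section 10.2 plans a log-rank test and does not return to the margin. The rates in 10.1 are for revision with no cause stated, while the primary endpoint in 4.1 is revision for aseptic loosening.
- *Radiographs dated differently from the scores.* Section 7.3 speaks of "assessing the last anterior-posterior and lateral knee radiographs compared with the first postoperative radiograph" and section 11.2 of "radiographic data from visits and radiographic follow-ups normally carried out during normal clinical practice", but section 3 and form 5 in section 8.1 tie the films to the last follow-up. The wording is ambiguous at most.
- *Sequential use of the inserts.* Nothing says whether one replaced the other or both were used throughout.
- *A matched design.* The single reference to pairing has no matching procedure or paired test behind it.

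**Conclusion.** The omission is certain from the text: non-randomised groups, only unadjusted and unpaired tests, recorded covariates unused for adjustment, and no bilateral rule. Its effect is unknown, because allocation, calendar overlap and bilateral share are not reported. Under the stated assumptions, confounding of the scores is the larger risk (error 14 to 41% for a bias of 0.1 to 0.2 SD). Clustering is modest and can go either way (1.7 to 8.8%). No magnitude is claimed for the log-rank analysis of the primary endpoint. The plan should be changed because a better analysis is available at little cost from data already collected. As planned, a between-group difference in scores could not be attributed to the insert.

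**What to change.** 1. **AKSS and FJS-12.** Make the main comparison a linear regression on insert group with age at surgery, BMI (from recorded weight and height), diagnosis and osteoporosis, with patient-clustered standard errors. Keep the t and Mann-Whitney tests as sensitivity analyses. State whether the telephone or the visit FJS-12 is analysed.
2. **Implant age.** Report the count of each insert per calendar year. Where the inserts overlap in calendar time, add time from surgery to assessment to the model. If use was largely sequential, report the models with and without that term and state that insert and period cannot be separated.
3. **Survival and binary outcomes.** Keep the 10.2 analyses on all knees. Account for bilateral patients by patient-clustered variance, or by a one-knee-per-patient sensitivity analysis with all events listed. State that few events limit covariate adjustment.
4. **Pairing.** Reconcile section 10.1 with 10.2: either describe the matching and analyse accordingly, or describe independent groups.
5. **Limits.** State that adjustment is partial. Sex, surgeon and preoperative AKSS are not named in section 8.1 (the annexed forms are not shown).

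The cost is SAP wording and modest programming, with no new data for the listed covariates. Software beyond GraphPad Prism, the only package named, may be needed. Adjusting for time since surgery widens the SE by about 3% at a 65/35 calendar split and 16% at 80/20. It would widen it by 89% under fully sequential use, which is why item 2 depends on overlap. A one-knee sensitivity analysis would use 9 to 23% fewer knees if 10 to 30% of patients are bilateral (1 − 1/1.1 and 1 − 1/1.3).
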